9.3.3 Secondary Endpoints

Secondary outcome measures are the effect of naloxegol versus usual care on; bowel movements per week, stool quality using the BSS,² occurrence and grade of AEs using the NCI CTCAE version 4.03,³ health related quality of life utilizing the PAC-SYM⁴ & PAC-QoL,⁵ and changes in patient reported pain using the BPI-sf.⁶

For variables in the secondary aim, we plan to use generalized linear mixed effects models to determine the impact of naloxegol on each endpoint over the course of 2 weeks for the initial treatment and crossover treatment phases of the study, achieved by including treatment group as a categorical covariate, and including a categorical time effect to account for a potential period effect. Counts of bowel movements per week will be assessed using a Poisson model. Stool quality (BSS, 7 point Likert-type scale), PAC-SYM (5 point Likert-scale), and PAC-QOL (5 point Likert-scale) will be assessed using an ordinal logistic model. The two parts of the BPI-sf (Intensity of pain and inference of pain) are calculated as the mean of several questions; as such they will be assessed as a continuous outcome with possible transformation for skewness if necessary.

To control for the multiple comparisons, a Bonferroni-Holm (e.g. Stepwise Bonferroni) method will be applied to the combined secondary and exploratory analyses, using an omnibus $\alpha = 0.05$.

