5.1.13.5 PAC-SYM Questionnaire

The PAC-SYM questionnaire¹² (**Appendix H**) will be used to assess patient quality of life. The PAC-SYM questionnaire is a 12-item questionnaire that evaluates the severity of symptoms of constipation in 3 domains (stool, rectal, and abdominal symptoms) on a 5-point Likert scale ranging from 0 (absent) to 4 (very severe) in the 7 days prior to assessment. The items of the instrument were developed through literature review and patient interviews. The PAC-SYM has been extensively validated for constipation and is available in several languages. The translations into local languages have been performed according to a linguistic validation process. The PAC-SYM is validated for a **7-day recall**, therefore, participants will be asked to complete this questionnaire every 7 days during the initial and crossover treatment periods, every 28 days during the optional extension phase and at the end of study visit. This questionnaire takes approximately 5 minutes to complete.

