5.1.13.6 PAC-QOL Questionnaire

The PAC-QOL questionnaire¹³ (**Appendix I**) will be used to assess patient quality of life. The PAC-QOL questionnaire is a 28-item self-report instrument designed to evaluate the burden of constipation on patient's everyday functioning and well being in the 2 weeks (14 days) prior to assessment. Each item is rated on a 5-point Likert scale ranging from 0 (not at all) to 4 (extremely). Development of the PAC-QOL items was informed by both clinician and patient focus groups and the primary validation study evaluated use of the PAC-QOL in the US, Netherlands, Belgium, Canada, and Australia using French and Dutch translations in addition to the original English language based instrument.¹³ This questionnaire takes approximately 5 minutes to complete. The instrument can be used to generate an overall score, but is also reported to assess 4 specific constipation-related domains, including: 1) worries and concerns (11 items), 2) physical discomfort (4 items), 3) psychosocial discomfort (8 items), and 4) satisfaction (5 items). The PAC-QOL is validated for a **2-week recall**, therefore, participants will be asked to complete this questionnaire every 14 days during the initial and crossover treatment periods, every 28 days during the optional extension phase and at the end of study visit. This questionnaire takes approximately 5 minutes to complete.

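### PAC-SYM and PAC-QOL are planned as if each were a single 5-point outcome, but the documents define no such patient-level score

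*Combined protocol and SAP*

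**What the plan says.** Section 9.3.3 (Secondary Endpoints) gives the model for the two constipation questionnaires: "PAC-SYM (5 point Likert-scale), and PAC-QOL (5 point Likert-scale) will be assessed using an ordinal logistic model". The Statistical Methodology entry of the synopsis carries the same assignment.

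The instruments themselves are described in Section 5.1.13. "The PAC-SYM questionnaire is a 12-item questionnaire that evaluates the severity of symptoms of constipation in 3 domains", with responses running from 0 to 4. "The PAC-QOL questionnaire is a 28-item self-report instrument", and there the text is explicit that the scale is per item: "Each item is rated on a 5-point Likert scale ranging from 0 (not at all) to 4 (extremely". On scoring, Section 5.1.13.6 says: "The instrument can be used to generate an overall score, but is also reported to assess 4 specific constipation-related domains". Appendices H and I reproduce the forms and show the 12 and 28 numbered items.

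In the sentence after the ordinal assignment, Section 9.3.3 turns to the BPI-sf. It says that its two parts "are calculated as the mean of several questions; as such they will be assessed as a continuous outcome", with transformation for skewness if needed. The Holm procedure then covers all secondary and exploratory analyses together.

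**The concern.** The label in Section 9.3.3 describes the response format of one item, but it is attached to a whole questionnaire. An ordinal logistic model for a 5-point outcome has four thresholds. That matches a single item and does not match any total, mean or domain score these instruments produce. The analyst is therefore told to fit a model to an outcome that the documents never construct.

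At stake is the analysis of secondary objective 4, which rests on these two instruments. Several different analyses could claim to follow the text: item by item, repeated items in one model, a rounded mean, or the full score treated as ordinal. They need not agree. In an open-label trial the choice should be fixed before data are seen. The number of tests these instruments add to the Holm family also depends on it.

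**Working it through.** The documents give no power or precision figure for PAC-SYM or PAC-QOL, so there is none to reproduce. The only design calculation concerns the primary endpoint (50 patients, 70% versus 85%, one-sided exact test). It reproduces: 41 or more completers gives an exact alpha of 0.040 and power of 0.791, against the stated 80%. It does not involve these instruments.

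**Step 1: possible values of each score.** A sum, or equivalently a mean, of k items each scored 0 to m takes k × m + 1 values. Item counts and ranges come from Sections 5.1.13.5 to 5.1.13.7 and Appendices H to J. For BPI-sf, I take intensity as the four pain ratings and interference as the seven interference ratings.

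| Score | Items | Item range | Possible values | Planned handling |
|---|---|---|---|---|
| PAC-SYM overall | 12 | 0–4 | 12 × 4 + 1 = 49 | ordinal, labelled 5-point |
| PAC-QOL overall | 28 | 0–4 | 28 × 4 + 1 = 113 | ordinal, labelled 5-point |
| BPI-sf intensity | 4 | 0–10 | 4 × 10 + 1 = 41 | continuous |
| BPI-sf interference | 7 | 0–10 | 7 × 10 + 1 = 71 | continuous |

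The four PAC-QOL domains have 11, 4, 8 and 5 items (11 + 4 + 8 + 5 = 28). Their sums take 45, 17, 33 and 21 values. None of these scores has five values.

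**Step 2: comparison with BPI-sf.** The number of values does not separate the two groups. PAC-SYM (49) lies between the two BPI-sf parts (41 and 71), and PAC-QOL (113) exceeds both. The plan's reason for treating BPI-sf as continuous, averaging over several questions, holds at least as well for 12 or 28 items as for 4 or 7.

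**Step 3: how sparse a cumulative-logit model on the full score would be.** Such a model needs one threshold fewer than the number of distinct values observed: at most 48 for PAC-SYM and at most 112 for PAC-QOL. Average observations per possible value = patients × periods × records per period ÷ possible values. I assume 50 patients, two periods and complete data.

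- PAC-QOL, one record per period: 50 × 2 × 1 / 113 = 100 / 113 = 0.88
- PAC-QOL, two records per period: 200 / 113 = 1.77
- PAC-SYM, one record per period: 100 / 49 = 2.04
- PAC-SYM, two records per period: 200 / 49 = 4.08

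The planned frequencies (PAC-SYM every 7 days, PAC-QOL every 14) correspond to the first and last lines. Dropout lowers all four.

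**Step 4: direction of the items.** In Appendix I, item 18 (feeling in control) and items 25 to 28 (satisfaction) are worded so that a high answer is favourable. The other 23 are worded so that a high answer is unfavourable. All use the same 0 to 4 coding. The protocol does not state how they are combined.

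**The case against.** The strongest reply is that Section 9.3.3 names a model family and mentions the response format only in parentheses. It does not say that the questionnaires are collapsed to five categories. A cumulative-link model can be fitted to a many-valued score. A single ordinal mixed model with items repeated within patient would use all the item data and still give one treatment test per instrument. This stands in part: the ordinal family is not invalid, and a fully specified ordinal model would be acceptable. It does not rescue the text, because neither version is specified and the only outcome named is a 5-point one that exists at item level.

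Three stronger readings are tempting, and the documents support none of them.

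- A reader might infer that the plan must either discard information by rounding or run 12 + 28 = 40 item tests inside the Holm family. The two ordinal models just described are further options. Section 9.3.3 lists the instruments, not their items, as endpoints.
- A reader might infer that the PAC-QOL effect will be diluted by a set percentage because favourable and unfavourable items cancel. That presumes an average taken without reversing items, which the plan never describes.
- A reader might infer from the silence on reversal that it will be omitted. PAC-QOL is a standard published instrument whose scoring rules may cover this. The silence shows only that the scoring rule is unstated.

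It is also fair to say that these are secondary outcomes in a pilot whose primary endpoint is completion.

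**Conclusion.** The point holds as a mismatch between the analysed outcome and the instrument. The plan assigns a 5-point ordinal outcome to questionnaires whose overall scores take 49 and 113 values, and no patient-level 5-category score is defined. Treating the full scores as ordinal would be workable in principle but thin. It would average about 0.9 observations per possible PAC-QOL value and about 4.1 for PAC-SYM, assuming 50 patients with complete data at the planned frequency. The different handling of BPI-sf in the next sentence has no stated reason and does not follow from the number of values.

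No numerical bias or power loss can be attached to this. That would need standard deviations and inter-item correlations, which the documents do not give, as well as a scoring procedure that they do not state. The consequence is confined to secondary endpoints. The primary test, its alpha and the sample size are unchanged.

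**What to change.** In Section 9.3.3 and in the synopsis:

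- Define the analysed outcome for each instrument as its overall mean score. Analyse it as continuous in the linear mixed model already planned for BPI-sf, with treatment and period effects. Each instrument then contributes one test to the Holm family. The synopsis mentions only a time-dependent arm covariate, so align it with the treatment and period terms of Section 9.3.3.
- State the scoring rule so that all items run in one direction, naming PAC-QOL items 18 and 25 to 28. Say how a questionnaire with unanswered items is scored.
- If domain scores are reported, say whether they are descriptive or counted under Holm.
- Name the record that represents each period. The Schedule of Events places PAC-QOL on Days 1 and 18, and after that only in the extension phase or at the end-of-study visit. A period effect alone does not settle which record stands for the crossover period.

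If the team prefers an ordinal analysis, the alternative is to specify it fully: the score or items used, the categories, and the one test per instrument.

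The cost is wording only, with no new data, visits or patients. The small downside is that a score bounded at 0 and 4 is treated as continuous. The transformation for skewness already allowed for BPI-sf can be extended to these scores.

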Treatment of OIC includes both prophylaxis and therapeutic treatment. Since opioids have the unintended consequence of slowing bowel motility, prophylaxis should begin at the initiation of an opioid regimen. Constipation prophylaxis can be approached in a stepwise additive fashion with stimulant laxatives such as senna (1-8 tabs/day) and bisacodyl (maximum 30 mg/day) as the agents of choice. However, patients must titrate these stimulant laxatives based on diet, exercise, fluid intake, and concomitant medication use. Consequently, titrating stimulant laxatives can result in under or overtreatment and be quite burdensome to patients.

Ideally, OIC is prevented, but when it does occur in spite of prophylaxis, it can be effectively treated with the addition of other classes of laxatives (e.g. osmotics, softeners). However, the most specific drug class to specifically reverse OIC is the peripherally acting μ -opioid antagonists. For example, methylnaltrexone (Relistor[®]) is a subcutaneous injection and treatment of OIC in patients with advanced medical illness¹¹ and alvimopan (Entereg[®]) has restricted approval for shortening the course of postoperative ileus.¹² Naloxegol (Movantik[®]), the most recently approved oral, peripherally acting, pegylated derivative of the μ -opioid receptor antagonist naloxone, has been evaluated in non-cancer pain and shown to reduce constipation without reducing opioid-mediated analgesia.¹³ With 25mg of oral naloxegol versus placebo subjects experienced an approximate 15% improvement in response rate (defined as at least 3 spontaneous bowel movements per week and at least one spontaneous bowel movement per week increase over baseline for at least 9 out of the 12 treatment weeks and 3

out of the last 4 treatment weeks during the double-blind treatment period.¹³

Opioid-Induced Constipation Management by UCSD Palliative Care Team

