2.2 Secondary Objectives

1. To determine the frequency of naloxegol versus usual care on OIC as defined by ≤ 3 bowel movements per week.
2. To evaluate naloxegol versus usual care on stool quality using the Bristol Stool Scale (BSS).²
3. To describe the adverse events associated with naloxegol when administered daily in this patient population and to compare the adverse events associated with Naloxegol with adverse events observed with usual care, using the National Cancer Institute Common Terminology Criteria for Adverse Events (NCI CTCAE) version 4.03.³
4. To evaluate health related quality of life utilizing the Patient Assessment of Constipation Symptoms (PAC-SYM)⁴ and Patient Assessment of Constipation Quality of Life (PAC-QOL).⁵
5. To evaluate changes in patient reported pain using the Brief Pain Inventory-Short Form (BPI-sf).⁶

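### One Holm correction covers the two BPI-sf pain scores together with all other secondary and exploratory tests, which makes a real loss of analgesia harder to detect

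*Combined protocol and SAP*

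**What the plan says.** Section 9.3.3 puts six outcomes in one secondary list: weekly bowel movements, stool form (BSS), "occurrence and grade of AEs using the NCI CTCAE version 4.03", PAC-SYM, PAC-QOL, and "changes in patient reported pain using the BPI-sf". For these, "we plan to use generalized linear mixed effects models to determine the impact of naloxegol on each endpoint". Pain gives two outcomes: "The two parts of the BPI-sf (Intensity of pain and inference of pain) are calculated as the mean of several questions" (the second part is evidently interference).

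The multiplicity rule follows: a Bonferroni-Holm "method will be applied to the combined secondary and exploratory analyses", at an overall level of 0.05. The Statistical Methodology row of the synopsis says the same. Neither place exempts a harm outcome, ranks the efficacy endpoints or states the number of tests.

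On AEs the plan is not clear. Secondary objective 3 in Section 2.2 aims "to compare the adverse events associated with Naloxegol with adverse events observed with usual care". Section 9.3.2, however, only describes looking at AE counts overall and by severity and names no test. Section 9.3.3 specifies a model for every other outcome on its list but none for AEs.

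Section 9.3.4 adds two exploratory comparisons, weekly pill counts and total health-care use. Patient preference gets only a confidence interval. The feasibility primary is tested separately (Section 9.3.1).

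**The concern.** Family-wise control protects against false claims of benefit. For an outcome measured to see whether the drug does harm, the error that matters more is missing a real effect, and a stricter threshold makes that error more likely. The rule then works in the drug's favour.

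Pain is such an outcome here. Naloxegol is an opioid antagonist given to patients who depend on opioids for cancer pain. Section 4.2 asks for monitoring for lost central analgesia after an overdose, and Section 8.1 explains why interference with analgesia should be limited at recommended doses. The reassurance cited in Section 1.1, that the drug was "shown to reduce constipation without reducing opioid-mediated analgesia", comes from non-cancer pain. The BPI-sf comparison is this trial's own evidence on the question in cancer patients.

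At stake is interpretation. If a Holm-adjusted pain result is not significant, part of the reason may be the size of the family and not the absence of an effect. The efficacy endpoints also meet a stricter threshold because harm and exploratory tests share their family.

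**Working it through.** **The plan's own power figure.** The only one is for the primary endpoint (Section 9.2): 50 patients, 70% against 85%, one-sided exact test at 0.05, 80% power. The smallest qualifying rule is 41 or more completers of 50, with exact alpha 0.0402 and power 0.791. The normal approximation gives N = 49.4. The figure is reproduced to within a point. No power or effect size is given for any secondary or exploratory endpoint.

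**Size of the family**, counting one treatment test per outcome:
- efficacy and symptoms: bowel movements, BSS, PAC-SYM, PAC-QOL = 4
- BPI-sf intensity and interference = 2
- AEs = 0 if descriptive only, 1 if tested once
- exploratory: pill counts, total utilization = 2

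The total is 8 or 9. It would be 13 if AE occurrence and grade were tested separately and utilization were split into its four types (4 + 2 + 2 + 5). It would be 7 if AEs were descriptive and the pill-count comparison could not be made; Section 5.3.3 schedules pill counts for naloxegol only.

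**Power for one real harm effect.** Assume 80% power at an unadjusted two-sided 0.05. The standardised effect is 1.960 + 0.842 = 2.802, and power at a threshold of 0.05/k is Φ(2.802 − z), where z is the two-sided critical value.

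| Tests k | Threshold 0.05/k | Power |
|---|---|---|
| 1 | 0.05 | 80% |
| 4 | 0.0125 | 62% |
| 5 | 0.0100 | 59% |
| 7 | 0.0071 | 54% |
| 8 | 0.0063 | 53% |
| 9 | 0.0056 | 51% |
| 13 | 0.0038 | 47% |

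The rows for 7, 8, 9 and 13 are first Holm steps. If all four efficacy tests are rejected first in the nine-test family, five tests remain and power is 59%. In the eight-test family four remain and it is 62%.

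**Check by simulation.** The full Holm procedure was run with 200,000 replicates at correlations of 0 and 0.5. With one real harm and all else null, power is 51% (nine tests) or 53% (eight). If all four efficacy effects are also real, each with 80% unadjusted power, it is 55% or 57%.

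**Power for one efficacy endpoint**, same assumed effect, simulated at both correlations:

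| Family | One real efficacy effect | All four real |
|---|---|---|
| As written, 9 tests | 51–52% | 54% |
| Without the 2 exploratory tests, 7 | 55% | 58% |
| Without the 3 harm tests, 6 | 57% | 61–62% |
| The 4 efficacy tests alone | 62% | 71–73% |

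Taken out of the nine-test family on their own, the two exploratory tests return about 3–4 points and the three harm tests about 5–8. In the eight-test family, removing the two exploratory tests returns about 4–6 points (53% to 57%, or 56% to 61–62%).

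**The case against.** The strongest defence is that one pre-specified, conservative family is coherent for an open-label pilot with many unpowered endpoints, and that Section 6.4 files the BPI-sf under quality of life, not safety. The first part stands: how far to restrict the family is partly a matter of preference. The second does not settle the matter, because Sections 4.2 and 8.1 themselves treat interference with analgesia as a possible effect of this drug.

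A reader might infer several stronger things that the documents do not support:
- **That AEs are definitely in the family, making at least nine tests.** The secondary list and objective 3 point that way; Section 9.3.2 and the missing AE model point the other way. Only the two pain tests are certain.
- **That the rule halves the chance of detecting harm.** A fall from 80% to 51–53% is a relative loss of 34–36%, and Holm's step-down softens it when other tests are rejected first.
- **That exploratory tests are the main reason efficacy loses power.** In the nine-test family they account for a few points; the harm tests cost more.
- **That safety oversight is weakened.** The six-monthly AE summaries to the DSMB (Section 10.6) and the descriptive AE review do not depend on Holm. They do not, however, replace the BPI-sf comparison.
- **That the sponsor will read a non-significant pain result as no difference.** No section says so; this is a risk, not a stated plan.

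**Conclusion.** The point holds for pain, and for AEs only if they are formally tested. As written, the rule cuts the chance of detecting a real loss of analgesia from an assumed 80% to about 51–53% with 8 or 9 tests, so the chance of missing it rises from 20% to 47–49%. If all four efficacy tests are rejected first, power recovers to about 59% in the nine-test family.

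The figures rest on an assumed effect size, two-sided testing, a normal approximation and one test per outcome. They show the cost of the rule; they are not a shortfall against any planned power. The feasibility primary is unaffected. This is a moderate problem of interpretation in a pilot, but the bias runs in the drug's favour and is cheap to remove.

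**What to change.** In Section 9.3.3 and the synopsis:
1. Take BPI-sf intensity, BPI-sf interference and any AE comparison out of the Holm family. Report each with an estimate and an unadjusted two-sided 95% confidence interval, and state that non-significance will not be read as absence of harm.
2. State whether AEs are formally tested. If they are, name the model; if not, say that Section 9.3.2 is the whole AE analysis.
3. Apply Holm to four named endpoints: bowel movements, BSS, PAC-SYM and PAC-QOL.
4. Report pill counts and health-care use unadjusted and labelled exploratory.

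This takes a few sentences and no new data, visits or patients. The cost is that harm and exploratory p-values no longer carry family-wise control and must be labelled so. If there were no true harm and the tests were independent, the chance of at least one false signal at 0.05 would be 1 − 0.95² = 10% for the two pain scores, and 1 − 0.95³ = 14% with one AE test added. A separate Holm family of three harm tests would avoid that, but power for one real harm would then be about 66% instead of 80%.
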